## ABSTRACT

Depression is present in about 20-30% of hemodialysis patients and is associated with morbidity and mortality. However, depression is inadequately diagnosed and treated among dialysis patients. This is due in part to the overlap between depressive symptoms (e.g. appetite change, trouble sleeping, feeling tired) and symptoms related to persistent metabolic derangements in hemodialysis patients (e.g. nausea, nocturnal cramps, feeling washed out after treatment). The overlap between depressive symptoms and dialysis-related complications makes it difficult to diagnose and therefore to treat depression. In addition, prescription of antidepressant medication may increase an already high pill burden and result in poor adherence. Moreover, the evidence base to guide depression treatment among hemodialysis patients is limited. In our previous work, we developed methods to use latent variables and structural equation modeling to isolate depressive symptoms. Other investigators have demonstrated that directly observed treatment enhances the effectiveness of tuberculosis and HIV treatment.

We now propose a cross-sectional study (Phase 1) followed by a randomized controlled trial (Phase 2) at 17 dialysis facilities. The cross-sectional study will involve assessments of depressive symptoms (using the PHQ-9 screening instrument) as well as dialysis-related complications (KDQOL) in about 1083 patients. We will then use structural equation modeling to develop and validate a hemodialysis-specific PHQ-9 (hdPHQ-9) that will isolate depressive symptoms. The trial will involve 216 patients with confirmed depression who will be randomly assigned to (a) directly observed weekly antidepressant treatment with fluoxetine or (b) referral to their nephrologists, their primary care physicians, or nearby mental health providers. The primary outcome of the trial will be remission of depression at 12 weeks. The trial results will also be used to compare the responsiveness of the PHQ-9 and the hdPHQ-9. We anticipate that the hdPHQ-9 will be a valid and responsive instrument that will isolate depressive symptoms in hemodialysis patients and ultimately improve the screening and diagnosis of depression. We also expect that directly observed weekly fluoxetine treatment will be an effective way to manage depression among hemodialysis patients.

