USING LATENT VARIABLES AND DIRECTLY OBSERVED TREATMENT TO IMPROVE THE DIAGNOSIS AND MANAGEMENT OF DEPRESSION AMONG HEMODIALYSIS PATIENTS

Date: October 3, 2017

NCT Number: NCT03390933

Statistical analyses

Develop and validate hemodialysis-specific depression screening instrument. We will begin by using graphs and descriptive statistics to summarize demographic and medical characteristics as well as scores on our measures of depression (PHQ-9) and dialysis complications. Next, we will perform exploratory factor analysis of the nine PHQ-9 items to determine how many latent factors represent aspects of depression. It has been hypothesized that the PHQ-9 has a two factor structure representing somatic and affective domains of depression. However, our previous work on depression and multiple sclerosis suggested a single factor structure. We will use an oblique (geomin) rotation and will examine the eigenvalues, which represent the variance accounted for by each underlying factor, in a scree plot. The number of eigenvalues ≥ 1 represent unique latent factors. We will also use parallel analysis to calibrate our decisions regarding meaningful eigenvalues. This approach computes eigenvalues from a random dataset via Monte Carlo simulation with the same number of observations and variables as used in the factor analytics model. Further, we will use model fit criteria such as chi-square, comparative fit index (CFI), Tucker Lewis fit index (TLI), root mean square error of approximation (RMSEA), and standardized root mean square residual (SRMR) statistical test values to help determine the measurement properties of our latent constructs.

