We will then use structural equation modeling to examine overlap between depressive symptoms and dialysis complications. Conducting these analyses involves four steps: 1) specifying the conceptual model, 2) estimating model parameters and assessing goodness of fit, 3) making any model modifications, and 4) testing hypotheses of interest. In particular, we will apply a measurement model with covariates which permits detection and adjustment for differential item functioning (DIF), i.e. when subgroups with the same latent trait have a different likelihood of responding to specific questions.⁷⁹ The initial model will include the factors representing aspects of depression, depressive symptoms, dialysis complications, and all the potential paths (referred to as DIF paths) connecting them. We will then make model comparisons and modifications to our initial model using multiple indices and statistics (e.g. chi-square, CFI, TLI, RMSEA, SRMR, modification indices) along with clinical input to establish the best fitting model, i.e. the most parsimonious model with all clinically relevant DIF paths of at least a small standardized path coefficient.⁸⁰ The results of these analyses will be standardized path coefficients which indicate the magnitude of the effect of one variable on another such as the impact of nocturnal cramps on sleep disturbance after adjustment for all other relationships in the model.²⁹ Both factor analysis and structural equation modeling will be performed with MPlus software.⁸⁰

For clinical use, we will develop a hemodialysis-specific PHQ-9 (hdPHQ-9) free of overlapping symptoms to isolate the underlying dimension of depression. We will extract factor scores from the latent construct (or constructs) representing depression in the final best fitting model to form this adjusted scale. A factor score is an individualized score on a latent construct representing a scale of interest. These factor scores will be linearly transformed to fit the range of the original PHQ-9 (i.e. 0–27) using a probability integral transformation to maintain the interpretation and thresholds of the PHQ-9. This one-to-one transformation will result in similar distributions of PHQ-9 and hdPHQ-9 scores in the sample. However, certain individuals will have sizeable differences between the two scores. We will also develop a web app that will allow users to enter information for a patient and will automatically calculate the hdPHQ-9 score.

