Finally, we will use bootstrapping in order to validate our hdPHQ-9. After developing our model

based on the entire sample, we will fit the model on a series of bootstrap datasets (each by resampling with replacement the same number of observations as the entire sample). From this

procedure we will: 1) obtain the average (as well as the 95% confidence interval) for each of the model parameters and fit indices across the bootstrap samples and 2) observe how the extracted hdPHQ-9 factor scores for each individual in the original data set vary across the models derived from each bootstrapped sample. Thus, bootstrapping validation can be used to understand if there is any bias and sampling variation in the model parameters and associated hdPHQ-9 scores due to overfitting in the final model.

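### The planned bootstrap averages and 95% intervals for the fit indices are shifted toward worse fit by case resampling itself, and should be dropped from the hdPHQ-9 validation summary

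*SAP*

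**What the plan says.** The relevant text is in the SAP under *Statistical analyses*. The paragraph on factor analysis names the fit criteria ("we will use model fit criteria such as chi-square, comparative fit index (CFI" and so on). The paragraph on structural equation modeling repeats the list for choosing and modifying the model: "chi-square, CFI, TLI, RMSEA, SRMR, modification indices".

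The closing paragraph describes validation. The model is developed on the whole sample and then refitted on bootstrap datasets, "each by resampling with replacement the same number of observations as the entire sample". The first planned output is to "obtain the average (as well as the 95% confidence interval) for each of the model parameters and fit indices across the bootstrap samples". The second is how each person's hdPHQ-9 factor score varies across the refitted models. The stated purpose is to detect "bias and sampling variation in the model parameters and associated hdPHQ-9 scores due to overfitting in the final model".

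The SAP mentions no transformation of the data to the model-implied covariance and no bias correction. It gives no estimator, no final df and no number of bootstrap samples.

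**The concern.** Case resampling imitates drawing new samples from the population, with the observed sample standing in for that population. That works for a loading or a path coefficient, because the bootstrap population has the sample estimate as its true value. It does not work for a measure of misfit. Sampling error alone prevents any sample from fitting the model exactly, even when the model is correct in the real population. In the bootstrap world that error becomes genuine misfit, and each resample adds its own error on top. Error is counted twice, and always in the direction of worse fit.

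The stake is the accuracy of a reported validation result. The SAP would present, as 95% confidence intervals for fit, ranges that are not centred on the quantity they describe. A reader who compares the full-sample fit with a poorer bootstrap average could take the gap for optimism in the fitted model, when the gap arises with no overfitting at all.

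**Working it through.** The SAP states no figure for the bootstrap, so there is none to reproduce. The check has an analytic part and a simulation.

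**Inputs**
- N = 1083, from the protocol abstract: "dialysis-related complications (KDQOL) in about 1083 patients".
- Nine items, from the SAP: "exploratory factor analysis of the nine PHQ-9 items".
- One factor: an assumption. The SAP leaves one or two factors open and says the team's earlier work in multiple sclerosis suggested one.
- df = 27 under that assumption: 9 × 10 / 2 = 45 variances and covariances, less 9 loadings and 9 residual variances.
- Maximum likelihood, loadings and category thresholds: assumptions.

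**Analytic rule**
1. Write T for the sample chi-square. Over case resamples, mean chi-square ≈ T + df.
2. RMSEA² = (T − df) / (df × N). Replacing T by T + df adds df / (df × N) = 1/N, so bootstrap RMSEA² ≈ RMSEA² + 1/N, whatever the df.
3. Here 1/N = 1/1083 = 0.000923.
   - RMSEA 0: √0.000923 = 0.030; chi-square 27 → 27 + 27 = 54.
   - RMSEA 0.051: √(0.0512² + 0.000923) = 0.060.
   - RMSEA 0.089: √(0.0885² + 0.000923) = 0.094.

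**Simulation, correct one-factor model, normal items** (60 data sets, 150 case resamples each)

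| Index | Sample mean | Bootstrap mean | Average 95% interval | Interval contains the sample's own value |
|---|---|---|---|---|
| Chi-square | 27.2 | 54.2 | 32.6 to 81.0 | 5% of data sets |
| RMSEA | 0.007 | 0.029 | 0.012 to 0.043 | 25% |
| CFI | 0.999 | 0.991 | 0.983 to 0.998 | 25% |
| TLI | 1.000 | 0.988 | 0.977 to 0.998 | 5% |
| SRMR | 0.014 | 0.020 | 0.015 to 0.025 | 13% |

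The bootstrap mean was worse than the sample value in every data set for all five indices. The interval contained the true RMSEA of 0 in 20% of data sets. Mean loading was 0.6306 in the sample and 0.6302 over resamples, so parameters are not affected. Two further simulations with the same N and df gave mean chi-square 27.8 → 54.8 and 28.3 → 55.1.

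**Four-category items treated as continuous, correct model** (60 × 150): chi-square 34.6 → 68.5, RMSEA 0.014 → 0.037, CFI 0.996 → 0.981.

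**Misspecified models, two-factor truth fitted with one factor** (25 × 150 each)
- RMSEA 0.051 → 0.059; CFI 0.971 → 0.961.
- RMSEA 0.089 → 0.093; CFI 0.905 → 0.896.
- The interval contained the sample value in every data set.

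**Possible repairs**
- *Bollen-Stine bootstrap* (data first transformed so that the model holds exactly). With a correct model, mean chi-square returns to 26.9. With the two misspecified models it is still 26.9 and 27.4, although their sample values are 104.9 and 256.8. It is a null reference for the exact-fit test and says nothing about the size of misfit.
- *Subtracting df from each bootstrap chi-square.* With T = df = 27 the bootstrap chi-square is approximately noncentral chi-square with 27 df and noncentrality 27. After subtraction its 95% range is 4.7 to 54.4. The sampling range of a chi-square with 27 df is 14.6 to 43.2. The ratio of widths is 49.7 / 28.6 = 1.7, so the centre is repaired but the interval is too wide.

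**The case against.** The strongest reply is about consequence, and most of it stands.

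- **Nothing is decided on bootstrap fit.** The number of factors and the model modifications are settled beforehand on full-sample indices. No threshold or go/no-go rule uses the bootstrap values. The hdPHQ-9 scores and the randomised comparison are untouched, and the error makes fit look worse, so it cannot falsely endorse the instrument. All of this is right.
- **The documents do not say that the fall in fit will be reported as overfitting.** A reader might infer it, because a drop from apparent to resampled performance is the usual sign of optimism and the paragraph gives overfitting as its concern. But that sentence speaks of "bias and sampling variation in the model parameters and associated hdPHQ-9 scores due to overfitting in the final model"; fit indices are not in it. A misreading is possible, but the SAP does not plan one.
- **The large figures need a model that holds exactly.** For a model with appreciable misfit the shift in RMSEA is under 0.01 and the interval still covers the sample value. This also stands. Against it, the SAP selects for good fit, and the relative distortion is largest there.
- **The simulated model is not the planned one.** The final model adds dialysis complications and differential item functioning paths, and a categorical-data estimator was not simulated. The chi-square and CFI figures are therefore illustrative. The direction should carry over, since the mechanism does not depend on maximum likelihood, and the 1/N shift in RMSEA² does not depend on df.

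None of this makes the planned intervals correct. The SAP commits to reporting them as 95% confidence intervals, and nothing elsewhere in the documents corrects them.

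**Conclusion.** The point holds as a defect in one reported output of the Aim A validation. Averages and percentile intervals of the fit indices over plain case resamples are shifted toward worse fit: chi-square by about its df, and RMSEA² by about 1/N = 0.000923. For a correct model at N = 1083 that doubles chi-square (27 to 54 at 27 df) and raises RMSEA from 0.007 to 0.029, with an interval that usually misses both the sample value and the true value. For misfitting models the shift is modest, 0.051 to 0.059 or 0.089 to 0.093. The specific figures rest on one factor, maximum likelihood, 27 df and assumed loadings; the direction and the 1/N rule do not rest on the df.

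It would go too far to conclude that the validation of the hdPHQ-9 as a whole is invalid. The bootstrap of parameters is not distorted by this mechanism, and no decision or trial result rests on bootstrap fit. The change is worth making because it is nearly free and keeps mislabelled intervals out of the published validation.

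**What to change.** In the bootstrap paragraph of the SAP, delete the fit indices from the first listed output, leaving the average and 95% interval for model parameters only. Keep the second output, the variation in individual hdPHQ-9 scores, as it is.

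Add that chi-square, CFI, TLI, RMSEA and SRMR will be reported from the full sample, with the analytic noncentral chi-square interval for RMSEA.

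If a bootstrap assessment of fit is still wanted, a Bollen-Stine bootstrap may be used for the p-value of the exact-fit test, and for nothing else: it should not supply averages or intervals of fit. Subtracting df from the bootstrap chi-squares should not be used to form intervals. Stating the estimator in the same revision would also help, since the SAP does not give it.

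The cost is about one sentence of SAP wording. No extra data are needed, and the resampling of parameters and scores goes ahead as planned.
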